Children with Attention-Deficit/Hyperactivity Disorder (ADHD) are typically treated with two types of medications with differing mechanisms of action: stimulants and non-stimulants. The stimulant Vyvanse (lisdexamfetamine, LDX), and the non-stimulant Intuniv (extended-release guanficine, GXR), are both FDA-approved treatments for ADHD in children. Clinical trials have shown that both medications are effective in reducing ADHD symptoms, although the neurobiological mechanisms by which Vyvanse and Intuniv produce these effects remain unknown. The aim of this study is to examine the mechanisms by which LDX and GXR reduce symptoms in children with ADHD. MRI scanning will be used to understand the structure and blood flow within the brains of children with ADHD treated with LDX and GXR.

A total of thirty (30) children with ADHD and ten (10) age- and sex-matched, healthy controls will be scanned at the beginning of the study. In this first part of the study, MRI findings will be compared between the groups (i.e., children with and without ADHD) to see whether brain functioning of children with ADHD differs from that of healthy children. In the second part of the study, the children with ADHD will be randomized (1:1 ratio) to receive treatment with LDX or GXR for six (6) weeks. In the first few visits of the treatment phase of the study, the study doctor may adjust the medication dose to optimize its effect. At the end of the study, the children with ADHD treated with LDX or GXR will have a second MRI scan. The findings of that second MRI scan will be compared to the first MRI scan in order to identify brain changes due to the medication. These second MRI scans will also be compared to the scans of the healthy controls.

We seek to examine whether treatment with LDX and GXR leads to changes in brain structure and function and thereby help to reduce symptoms of ADHD. Furthermore, we will examine how these two drugs differ in yielding their therapeutic effect. This may inform how specific changes in the brain may underlie improvement in the various symptoms of ADHD.

Background, Significance and Rationale

Background, Significance and Rationale

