Exploratory Aim: To examine the concordance between the Pubertal Development Scale (Petersen et al., 1988) and the Tanner Stages and the acceptability of these measures to participants and their parents/guardians. Parent report will be collected if participants are <11 years, and self report will be collected if participants are 11 years or older.

Description of Subject Population

Sample #1

Specify subject population

Children with ADHD

Number of completers required to accomplish study aims

30

Projected number of subjects who will be enrolled to obtain required number of completers

80

Age range of subject population

6-17 years

Sample #2

Specify subject population

Healthy Control Children

Number of completers required to accomplish study aims

30

Projected number of subjects who will be enrolled to obtain required number of completers

80

Age range of subject population

6-17 years

Gender, Racial and Ethnic Breakdown

In terms of gender, we expect the majority of children with ADHD to be male (approximately 80%), which reflects the fact that ADHD is more common in boys than in girls.

In terms of ethnic breakdown, this sample will represent a wide array of racial and ethnic backgrounds that are representative of both the population in the Washington Heights area and New York City at large (e.g., 60% White, 40% Hispanic/Latino of any race, 20% Black/African American, 5% Asian, 10% other race, 5% two or more races). Additional efforts will be made to diversify the population of participants by advertising in community/neighborhood newspapers throughout New York City and surrounding areas. We will first seek IRB approval prior to releasing these advertisements.

Description of subject population

The subject populations will consist of:

- Children with ADHD
- Healthy control children, who will be matched on age and sex.

Recruitment Procedures

Describe settings where recruitment will occur

Study Recruitment Websites

Participants will be recruited through research study recruitment websites such as RecruitMe and Clinicaltrials.gov.

Flyers and Brochures

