- **For ADHD participants with a history of tic disorder:** Based on the information gathered from the medical history and the psychological assessments during the initial visit(s), the study doctor will carefully weigh the risks and the benefits of LDX treatment with the parent/guardian of the child participant. The decision to randomize the participant or to remove him/her from the study will depend on the study doctor's clinical judgment and the preferences of the parent/guardian. The study doctor will follow the same clinical practice guidelines for evaluating and treating co-occurring ADHD and tic disorder as doctors in the community. If the study doctor and parent/guardian agree that the benefits of potential treatment with LDX outweigh the risks, then the participant will proceed to the randomization procedures outlined below.
- **For female ADHD participants who have had their first period:** Female ADHD participants who have had their first period and who are sexually active will need to: (1) be using contraception prior to beginning treatment, and (2) agree to continue using contraception throughout the course of treatment in order to participate in the study. The study doctor will talk to female participants who have had their first period about ways to prevent pregnancy, the potential risks of the study medications on pregnancy (as part of consent/assent), as well as the limitations of urine pregnancy testing. Participants and their parents/guardians will be advised to notify the researcher immediately should they suspect that the participant is pregnant. If a participant is suspected to be pregnant, we will perform another pregnancy test to determine if she should continue the study. In case of pregnancy, the participant will discontinue the study early and we will provide assistance with obstetrical follow-up.

2. Randomization Procedures

Eligible ADHD participants will be randomized to treatment with LDX or GXR using a 1:1 ratio. Participants, research staff, and the study doctor will NOT be blinded to treatment.

3. Medication Management

Following randomization, participants will be taken through a medication management protocol over the subsequent 6 weeks. This protocol will begin with 4 weeks of medication titration, which will be followed by 2 weeks of medication maintenance. Titration will help the study doctor determine the minimum dose of medication necessary to achieve treatment response.

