Title: An fMRI Study of Stimulant vs. Non-Stimulant Treatment of ADHD

NCT Number: NCT02259517

Document Date: July 10, 2020

Hypothesis Testing

Primary Objective: Vyvanse (lisdexamfetamine; LDX) reduces impulsivity by normalizing cognitive control and reward processing circuits, whereas Intuniv (guanfacine, extended-release; G-EX) reduces impulsivity by normalizing cognitive control but not reward processing circuits.

We will first examine whether there are significant pre- vs. post-treatment changes in cognitive control and reward processing circuits. **Task-based functional MRI (fMRI) analyses:** We will enter each participant's task-related contrast map into a 2×2 repeated measures factorial model, treating Time as a repeated measure with two levels (pre- and post-treatment), and Treatment as a between group factor with two levels (LDX and G-EX). We will isolate an interaction term (Time \times Treatment) to determine differential effects of treatment on task-related activation and then conduct post-hoc t- tests to determine the nature of the interaction. **Resting-state functional connectivity MRI (Rs-fcMRI) and Diffusion Tensor Imaging (DTI):** Analyses will be similar to those for task-based fMRI, but dependent variables will be seed based connectivity and FA maps.

For mediation analysis of treatment effects, we first estimate the changes in cognitive control and reward processing circuits that result from treatment (described in paragraph above). We then establish that the changes in these circuits, in turn, affect impulsivity, while controlling for treatment group. To estimate **path a (Fig. 1)**, we will use a linear regression model with pre-post

[figure not shown]

Figure 1 Mediation Model

changes in cognitive control and reward processing circuits as the outcome variable and treatment as the predictor variable. If we find a significant effect of treatment on both reward and cognitive control circuits, we will pursue multiple mediation analyses; otherwise, we will include only the circuit in which there is a significant effect of treatment. To estimate **path b**, we will use a linear regression model with pre-post change scores in impulsivity (based on parent report) as the outcome and

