pre-post change in cognitive control or reward processing circuits as primary predictors, while controlling for baseline impulsivity and treatment group. The mediation effect is then estimated by taking the product of the estimates for **path a and b** and using the bootstrap method to obtain standard errors, confidence intervals, and the test for statistical significance.

To test whether treatment effects on cognitive control or reward processing circuits are specific in mediating improvements in impulsivity, we will explore whether treatment-related changes in other neural networks also mediate the effect of treatment on impulsivity. We will first screen these additional neural networks based on a significant effect of treatment on connectivity within these networks. Only networks that show significant change with treatment will be added to the multiple mediation analyses described above. The indirect effects of the cognitive control or reward processing circuits will be tested in the existence of the mediation effects of other neural networks using the bootstrapping method.

Power: Power for detecting the mediation effect depends on the size of the associations between (a) treatment group and changes in cognitive control and reward processing circuits, and (b) changes in cognitive control and reward processing circuits and changes in impulsivity. Based on tabulated recommendations for sample sizes needed to test mediation effects, with a sample size of $n=60$, we have more than 80% power to detect a significant mediation effect with medium effect size of both paths a and b.

Secondary Objective: ADHD patients with baseline MRI anomalies within reward processing circuits will respond to Vyvanse, but not Intuniv, treatment. Conversely, ADHD patients with baseline MRI anomalies that are circumscribed to cognitive control circuits (i.e., reward processing comparable to healthy controls) will predict response to either Intuniv or Vyvanse.

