We will test the moderation effect of the baseline MRI measures cognitive control and reward processing circuits on the treatment response. We will use linear regression models with pre-post change scores in impulsivity measures as outcomes and Group, baseline measures of cognitive control and reward processing circuits measured in predefined regions of interest (ROIs), and their interactions as predictors. Likelihood ratio tests will be used to test the effect of moderation with combination of multiple brain imaging measures.

Power: With sample size of $n=60$, the minimum detectable effect size of Cohen's f^2 is 0.09 (smaller than medium effect size 0.15) with 80% power for a two-sided test at the 5% significance level. If the effect size of interactions between baseline measures within cognitive control and reward processing circuits and Group is greater than f^2 is 0.09, we would be able to detect such effect size.

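### Both SAP power statements assume 60 children, but the protocol requires only 30 treated completers, and the detectable f² of 0.09 is wrong even at 60

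*SAP*

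**What the plan says.** The SAP's Primary Objective power paragraph states that "with a sample size of $n=60$, we have more than 80% power to detect a significant mediation effect", provided both paths have a medium effect. It gives no numerical value for medium and refers to tabulated recommendations. The Secondary Objective power paragraph states: "With sample size of $n=60$, the minimum detectable effect size of Cohen's f^2 is 0.09". It specifies 80% power and a two-sided 5% test, and notes that 0.09 lies below the medium value of 0.15.

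The models behind these statements are set out in the same document. The imaging model has "Treatment as a between group factor with two levels (LDX and G-EX") and time before and after treatment as the repeated measure. Path a regresses circuit change on treatment. Path b regresses impulsivity change on circuit change, adjusting for baseline impulsivity and treatment. For moderation, "We will use linear regression models with pre-post change scores in impulsivity measures as outcomes", with Group, the baseline circuit measures and their interactions as predictors.

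In the protocol's Description of Subject Population, the entry "Number of completers required to accomplish study aims" is 30 for children with ADHD and a separate 30 for healthy controls. The entry "Projected number of subjects who will be enrolled to obtain required number of completers" is 80 for each group. The Lay Summary says: "A total of thirty (30) children with ADHD and ten (10) age- and sex-matched, healthy controls will be scanned". Under Randomization Procedures, "Eligible ADHD participants will be randomized to treatment with LDX or GXR using a 1:1 ratio". The Follow Up Evaluation and MRI Scan section schedules a second assessment for ADHD children only.

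**The concern.** There are two separate faults.

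First, 60 does not match the protocol's number for the group these models can use. Healthy controls have no drug arm, no second scan and no change score. They can help define what a normal circuit looks like, but they add no observations to path a, path b or the Group-by-baseline interaction. Sixty happens to equal 30 ADHD plus 30 control completers; if that is its source, it is the wrong count for these models. Neither document says.

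Second, the secondary power statement supplies all its own inputs, and 0.09 does not follow from them.

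Both objectives predict that one drug has an effect the other lacks. A study believed to have 80% power that in fact has far less may have a null result read as evidence against the mechanism, or as confirmation of the predicted absence.

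**Working it through.** **Moderation: attempt to reproduce 0.09.** Inputs from the SAP are n = 60, two-sided α = 0.05 and power 0.80. The test of u added regression terms has power P[F′(u, v, λ) > F₀.₉₅(u, v)], with λ = f²·n.

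- One interaction (Group, one baseline circuit, their product): u = 1, v = n − 4.
- Both circuits tested jointly (Group, two circuits, two products): u = 2, v = n − 6. This is the simplest form of the SAP's likelihood ratio test on several imaging measures.

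| n | Detectable f², 1 df | Detectable f², 2 df | Power at f² = 0.09 (1 / 2 df) | Power at f² = 0.15 (1 / 2 df) |
|---|---|---|---|---|
| 60 | 0.135 | 0.170 | 63% / 51% | 84% / 75% |
| 30 | 0.282 | 0.365 | 35% / 26% | 53% / 41% |

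Hand check for 1 df: the required λ is about 7.85, and 7.85/60 = 0.131, close to the exact 0.135.

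Other conventions tried at n = 60 do not give 0.09:

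- One-sided 5% test: 0.103–0.106.
- λ = f²·v in place of f²·n, 1 df: 0.140–0.151.
- 0.09 read as a partial R²: f² = 0.09/0.91 = 0.099, with power 67% two-sided or 78% one-sided.

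The smallest n with 80% power at f² = 0.09 is 90 (1 df) or 111 (2 df). If all 80 projected ADHD children completed, the 1-df figure would still be 0.101.

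**Which n applies.** Required ADHD completers are 30; at 1:1 that is 30/2 = 15 per arm. Sixty completers from 80 enrolled would need 60/80 = 75% completion. The Concurrent Research Studies section allows ADHD data to be shared from two other protocols, but does not describe those children as randomised to LDX or guanfacine, so it does not supply the 60.

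**Mediation.** Because medium has no stated value, these are ranges under assumptions. Trials were simulated with 1:1 treatment and path b adjusted for treatment and a baseline covariate (1,500 trials, 600 bootstrap draws each). Cells show power for the joint significance test / percentile bootstrap / bias-corrected bootstrap.

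| Assumed medium effect | n = 30 | n = 60 |
|---|---|---|
| path a d = 0.5, path b r = 0.30 | 8 / 9 / 17% | 29 / 30 / 40% |
| path a d = 0.5, path b f² = 0.15 | 11 / 12 / 19% | 36 / 36 / 47% |
| r = 0.30 on both | 12 / 13 / 22% | 40 / 40 / 52% |
| f² = 0.15 on both | 25 / 25 / 36% | 68 / 67 / 76% |
| r = 0.39 on both | 33 / 33 / 46% | 79 / 79 / 85% |

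The last row is the most favourable because r = 0.39 means f² = 0.39²/(1 − 0.39²) = 0.152/0.848 = 0.179, above the 0.15 that the SAP itself calls medium. If 0.39 is taken instead as a slope with unit residual variance (f² = 0.39² = 0.152), power at n = 60 is 66–75%.

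A simpler bound applies too. The SAP carries a circuit into mediation only if treatment significantly affects it, so for any one circuit power cannot exceed that of path a. Path a alone has 28% power (d = 0.5) or 54% (f² = 0.15) at n = 30, and 49% or 84% at n = 60.

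**The case against.** The figure of 30 is a required minimum, not a cap, and 80 ADHD children may be enrolled. The hypotheses written in the protocol compare ADHD children with controls; the mediation and moderation models appear only in the SAP, so 30 may never have been sized for them. The Lay Summary is weak support, since its 10 controls conflict with the 30 required elsewhere and it may be out of date. All of this is fair. It means the analysed number might exceed 30, not that 60 is planned. The continuation report's 24 completers of 38 enrolled does not settle it, because it mixes the two groups and enrolment was still under way.

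On the moderation figure, the remark that the detectable effect is below 0.15 does survive at n = 60 for a single interaction (0.135). It fails for two interactions tested jointly (0.170) and for either test at n = 30. The SAP does not say which test its power statement describes.

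On mediation, the tabulated source is not available here and medium is undefined, so more than 80% at n = 60 cannot be ruled out; one reading reaches 85%. That part stands as an unsupported claim at n = 60. At n = 30 no reading tried exceeds 46%.

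**Conclusion.** The concern holds on both counts. The f² of 0.09 is wrong from the SAP's own inputs: 0.135 or 0.170 is correct at n = 60, and no completer count up to the projected 80 gives 0.09. This result needs only the standard noncentral F calculation; the 2-df figure further assumes two circuits in the joint test.

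The 60 is not reconciled with the 30 ADHD completers the protocol requires. At 30, the detectable f² roughly doubles again to 0.28 (1 df) or 0.365 (2 df), and mediation power is 8–46% against the stated 80% or more. The mediation range depends on the assumed effect sizes and the bootstrap type; the mismatch in n and the f² error do not. Both of the SAP's formal power claims are affected, so this should be corrected before the analysis.

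**What to change.** 1. State one number in both documents: ADHD children with data before and after treatment who will enter the LDX versus guanfacine models. Bring the Lay Summary, the Description of Subject Population and both SAP power paragraphs into line with it, and say how it was derived.
2. Correct the detectable f² whichever number is kept, and say whether it refers to one interaction or a joint test: about 0.135 (1 df) or 0.17 (2 df) at 60; about 0.28 or 0.365 at 30.
3. Restate mediation power at that number, with numerical effects for paths a and b, the bootstrap type, and the requirement that path a be significant first.
4. If the number is 30, present mediation and moderation as estimates with confidence intervals and drop the claim of 80% power. The SAP already plans bootstrap intervals for the mediation effect.

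Cost: if 30 stands, text only, with a less favourable power statement and no extra enrolment. If the sponsor confirms 60, the protocol's required-completer figure must also change; that fits the projected enrolment of 80 if at least 75% complete, and the f² must still be corrected.

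### The SAP's claim of more than 80% mediation power at n=60 cannot be reproduced from the only effect size and alpha it states; those inputs give about 64–77% with a bootstrap interval

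*SAP*

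**What the plan says.** The SAP's Primary Objective tests mediation as the product of two regression coefficients. Path a is the effect of treatment on circuit change. Path b is the effect of circuit change on change in parent-reported impulsivity, estimated "while controlling for baseline impulsivity and treatment group". A circuit enters the mediation model only if treatment affects it significantly, so path a acts as a gate. The product is then assessed "using the bootstrap method to obtain standard errors, confidence intervals, and the test for statistical significance". The text does not say which of these three outputs decides, or which kind of bootstrap interval is meant.

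The Power paragraph under the Primary Objective gives its source as "Based on tabulated recommendations for sample sizes needed to test mediation effects" and concludes that, at n=60, "we have more than 80% power to detect a significant mediation effect with medium effect size of both paths a and b". The table is not named, medium is not given a number, and no alpha or sidedness is stated.

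The Power paragraph under the Secondary Objective (moderation) is the only place with numbers. It describes its detectable f² of 0.09 as "smaller than medium effect size 0.15", and it specifies "80% power for a two-sided test at the 5% significance level".

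**The concern.** A mediation effect counts as detected only if both paths are found. If each path has power a little above 80%, the chance of finding both is clearly below 80%. For the joint chance to reach 80%, each path needs about √0.80 = 0.894. At n=60 a single regression coefficient with f² = 0.15 has power of about 0.84. That fits the wording of the claim for one path, but not for the product that the SAP will test.

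This is the only power statement for the primary objective. If it is too favourable, readers will be told that a medium mediation effect would very probably be found, when the test misses it roughly a quarter to a third of the time with a bootstrap interval and more than half the time with a test based on the bootstrap standard error. The unspecified bootstrap also leaves a choice open that moves power by about 30 points.

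**Working it through.** **Inputs**
- n = 60, from the SAP's mediation power statement. Allocation is 1:1 (Protocol, Randomization Procedures), so 30 per arm.
- Medium effect: f² = 0.15 on each path. *Assumed*, taken from the moderation power paragraph. It equals a partial correlation of √(0.15/1.15) = 0.361, or a slope of √0.15 = 0.387 with residual SD 1. For path a, with treatment coded ±1, the arms differ by 2 × 0.387 = 0.775 SD.
- Two-sided 5%. *Assumed*, from the same paragraph.
- Path a: treatment only, 58 residual df. Path b: circuit change, treatment and baseline impulsivity, 56 residual df.

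**The plan's own figure.** It cannot be reproduced directly, because its table, metric, test and alpha are not given. The nearest match is the power of a single path.

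**Single path (noncentral F)**
Noncentrality λ = n × f² = 60 × 0.15 = 9.
- Path a: P(F(1, 58; λ=9) > 4.007) = 0.839
- Path b: P(F(1, 56; λ=9) > 4.013) = 0.838

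**Both paths (joint test)**
The two estimates are treated as independent: 0.839 × 0.838 = 0.703. By the same formula, 80% jointly needs n = 71 at f² = 0.15 (0.802; n = 70 gives 0.794), or f² of about 0.18 at n = 60 (0.898 × 0.898 = 0.806).

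**Simulation of the SAP's model**
It used 30 per arm, with path b adjusted for treatment and a baseline covariate. Runs were 4,000 trials × 1,000 resamples and 8,000 trials × 2,000 resamples. Monte Carlo standard error is below 1 point, e.g. √(0.68 × 0.32 / 8,000) = 0.005.

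| Decision rule, n=60, f²=0.15, two-sided 5% | Power |
|---|---|
| Joint significance of a and b | 68% (70% by formula) |
| Percentile interval | 64–68% across model variants |
| Percentile interval, with the gate on path a | 66–67% |
| Bias-corrected interval | 73–77% |
| Bias-corrected interval, with the gate on path a | 72–73% |
| z-test on the bootstrap standard error | 44–46% |

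The simulated joint figure is slightly below 0.703 because path b is estimated net of treatment and the covariate. Its simulated power is 0.81; path a's is 0.85.

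**What would reach 80%**
- Larger effects at n=60: percentile interval 76% at f² = 0.18, about 80% at 0.19 and 83% at 0.20; bias-corrected 84% at 0.18.
- A one-sided 5% test (90% interval) at f² = 0.15: 78–80% percentile, 84–87% bias-corrected.
- More patients at f² = 0.15, two-sided: about 76 (percentile), or about 66 (bias-corrected, ungated).

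**Other readings of medium (assumed), n=60, two-sided 5%, percentile to bias-corrected**
- r = 0.3 on both paths: 41–53%
- d = 0.5 on path a, f² = 0.15 on path b: 36–47%
- d = 0.8 on path a, f² = 0.15 on path b: 70–78%

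**Type I error when path a is zero**
- Percentile: about 3–4%
- Bias-corrected: about 7% ungated, about 4% with the gate
- Test on the bootstrap standard error: about 1%

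**The case against.** The strongest reply is that both key inputs are borrowed. The mediation paragraph does not define medium. The value 0.15 is a parenthesis in a paragraph about a different analysis, and the two-sided 5% level is stated only there. The cited table may use another metric, another test or another alpha, and it cannot be consulted. With a one-sided 5% test, the bias-corrected bootstrap passes 80% and the percentile interval is about at 80%. This objection stands as far as it goes: the result is conditional, and the documents do not support a flat statement that the SAP defines medium mediation as f² = 0.15 and then contradicts itself. It does not rescue the sentence, which gives none of the inputs under which it would be true.

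Three stronger readings are also tempting and should not be drawn.
- A reader might infer that the claim could hold only with f² near 0.18 and a bias-corrected interval. It could hold in other ways: the percentile interval also reaches 80% at f² of about 0.19.
- A reader might infer that choosing the bias-corrected bootstrap would inflate type I error to 7%. That is the ungated figure; under the SAP's own gate it is about 4%.
- A reader might infer that the sponsor will take a null result as evidence against the mechanism. Neither document says how a null would be interpreted.

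Preferring the percentile interval is also a judgement. What the SAP lacks is any named choice.

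**Conclusion.** The concern holds in conditional form. Assuming f² = 0.15 on both paths and a two-sided 5% test, the only convention the SAP states, power at n=60 is about 70% by the joint test, 64–68% by percentile bootstrap, 73–77% by bias-corrected bootstrap (72–73% gated) and about 45% by a z-test on the bootstrap standard error. No version reaches 80%. The shortfall is between 3 and 16 points for the bootstrap intervals and about 35 points for the test on the standard error, well beyond simulation error.

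Confidence is high in the calculation given these inputs. It is lower on what the authors meant by medium, since their table is not named. The point takes n=60 as given and is separate from whether 60 is the right number. It changes no estimand and no patient procedure, so it is a should-fix.

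**What to change.** 1. Replace the mediation power sentence with one that carries its inputs, for example: *With n=60, a two-sided 5% test and f²=0.15 on both paths, power is about 67% (percentile bootstrap interval); 80% power requires f² of about 0.19 on both paths.* If the authors meant another effect size or alpha, they should state it, name the table and give the matching figure.
2. State which single bootstrap result decides significance. The percentile interval is one suitable choice, with type I error of about 3–4% when path a is zero. If the bias-corrected interval is chosen, quote its power with the path a gate applied.
3. Recompute by the same method for the number of randomised ADHD completers finally adopted. The Protocol (Description of Subject Population, Sample #1) asks for 30 ADHD completers, and only children with ADHD are randomised. At n=30 the same inputs give about 26% (percentile) to 38% (bias-corrected), so the example sentence should not be adopted until n is settled.

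The cost is SAP wording and one short simulation. The stated power becomes less favourable; nothing in trial conduct changes.

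### The planned interaction test cannot by itself support the secondary claim that children with reward-circuit anomalies do not respond to Intuniv

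*SAP*

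**What the plan says.** The SAP's Secondary Objective makes statements about each drug separately. Children with a reward-circuit anomaly come first: "ADHD patients with baseline MRI anomalies within reward processing circuits will respond to Vyvanse, but not Intuniv, treatment". Children whose anomaly is "circumscribed to cognitive control circuits (i.e., reward processing comparable to healthy controls) will predict response to either Intuniv or Vyvanse" come second.

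The analysis paragraph that follows describes one approach: "We will test the moderation effect of the baseline MRI measures cognitive control and reward processing circuits on the treatment response". The outcome is a continuous change score: "We will use linear regression models with pre-post change scores in impulsivity measures as outcomes". The predictors are Group and baseline circuit measures "measured in predefined regions of interest (ROIs), and their interactions as predictors". The test is given as "Likelihood ratio tests will be used to test the effect of moderation with combination of multiple brain imaging measures". The power paragraph says "the minimum detectable effect size of Cohen's f^2 is 0.09" at n=60 and applies this figure to the interactions only.

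For this objective the SAP gives no arm-specific estimate, no bound for non-response, no definition of a responder, and no ROI value at which an anomaly begins or at which reward processing counts as comparable to controls.

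**The concern.** The hypothesis and the test address different quantities. Non-response to Intuniv is a statement about the mean change in one arm at one kind of baseline. A Group-by-baseline interaction is the difference between the two drugs' slopes on the baseline measure. It can be large when Intuniv does nothing for anomalous children, and also when Intuniv helps them and Vyvanse helps them more.

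The second half of the objective has the same gap. Response to either drug is also a within-arm statement, and neither a significant nor a null interaction establishes it.

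If the interaction were read as confirming the objective as worded, a drug on which these children improve could be described as one to which they do not respond.

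**Working it through.** **The plan's own figure.** Inputs from the SAP's second power paragraph: n=60, 80% power, two-sided 5%, minimum detectable f² of 0.09. With noncentrality f² × n, the normal approximation for one interaction term is (1.960 + 0.842)²/60 = 7.85/60 = 0.131. The noncentral F gives 0.135 for one term and 0.170 for two tested jointly. The 0.09 is not reproduced. That is a separate matter. What counts here is that the power statement concerns interactions only.

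**Step 1: what the interaction contains.** Let T=1 for Vyvanse and T=0 for Intuniv, R be the reward measure and C the cognitive-control measure:

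y = b0 + b1·T + b2·R + b3·C + b4·T·R + b5·T·C + error.

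- Intuniv mean at (r, c): b0 + b2·r + b3·c.
- Reward interaction: b4, the Vyvanse slope minus the Intuniv slope.

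Add a constant k to every Intuniv child, that is k(1 − T). Then b0 becomes b0 + k and b1 becomes b1 − k. The terms b2 to b5 and all residuals are unchanged, so the likelihood ratio statistic is unchanged too.

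**Step 2: numerical check of step 1.** One simulated data set, n=60, residual SD 1, anomaly coded as high R:

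| Added to all Intuniv children (SD) | b4 | Likelihood ratio statistic | Intuniv mean at R=+1 (SD) |
|---|---|---|---|
| 0 | 0.796 | 14.03 | 0.35 |
| 0.5 | 0.796 | 14.03 | 0.85 |
| 1 | 0.796 | 14.03 | 1.35 |
| 2 | 0.796 | 14.03 | 2.35 |

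Adding benefit only to Intuniv children with R above 0 does change the test. With 0, 0.5 and 1 SD added, b4 falls from 0.80 to 0.56 to 0.32, and the joint likelihood ratio p-value rises from 0.0009 to 0.005 to 0.02. It is still significant each time, while the predicted Intuniv mean at R=+1 rises from 0.35 to 0.83 to 1.32 SD.

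**Step 3: how often this happens under the SAP's hypothesised pattern.** The effect sizes are assumptions, since the documents give none:

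- Vyvanse improvement is 1.6 SD at every baseline value.
- Intuniv improvement is 1.6 SD at z=+1 (reward processing normal) and r at z=−1 (anomalous), so its slope is (1.6 − r)/2, which is 0.8 at r=0.
- Residual SD is 1, allocation 1:1, two ROIs correlated 0.3, both interactions fitted.
- The test is a two-sided 5% t-test of the reward interaction, counted when significant in the hypothesised direction.

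| True Intuniv improvement at z=−1 (SD) | Significant, n=60 | Significant, n=30 |
|---|---|---|
| 0 | 77% | 43% |
| 0.3 | 60% | 30% |
| 0.5 | 48% | 23% |
| 0.8 | 28% | 15% |
| 1.6 (no interaction) | 3% | 2% |

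The n=60 column follows the SAP. The n=30 column follows the 30 ADHD completers in the protocol's Description of Subject Population. With 6,000 trials per cell the simulation error is about √(0.48 × 0.52/6000) = 0.6 percentage points.

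**Step 4: what the same model can say about the Intuniv arm.** At z=−1 the average 95% half-width of the Intuniv mean is about 0.55 SD at n=60 and 0.85 SD at n=30 (median about 0.82 at n=30).

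**Step 5: other text that might fill the gap.**

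- The post-hoc t-tests in the SAP's Primary Objective follow the Time-by-Treatment imaging interaction, not clinical response.
- The CGI-I definition of response in the protocol's titration paragraphs guides dosing; the moderation model does not use it.
- Healthy controls complete the baseline scan, but the moderation model has no control reference.

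**The case against.** Three stronger readings are tempting, and the documents do not support them.

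First, a reader might infer that the test gives the same result whether or not Intuniv works in anomalous children. That is true only for a shift shared by the whole Intuniv arm. The SAP's hypothesis implies a flat Vyvanse response and an Intuniv response that depends on baseline. Under that pattern significance at n=60 falls from 77% to 28% as Intuniv improvement in those children rises from 0 to 0.8 SD. The test does carry some information.

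Second, a reader might infer that the model is wrong or cannot estimate the claimed quantity. It can: the intercept, main effects and interactions give each arm's mean change at any baseline value. What is missing is the planned contrast, the values at which to take it and a rule for interpreting it.

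Third, a reader might infer that the trial will report a significant interaction as proof of non-response, or that the objective is a prescribing rule. The SAP says only that moderation will be tested, and the protocol's Background describes the aim as exploring predictors of response.

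Two further objections stand. The trial is open label with no placebo arm (protocol, Randomization Procedures), so within-arm change mixes drug effect with time, expectation and regression to the mean. The randomised drug difference is the cleaner quantity. Also, the percentages above use a single-coefficient test, whereas the SAP names likelihood ratio tests on combined measures; the invariance in steps 1 and 2 holds for both.

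**Conclusion.** The point holds as a mismatch between the claim and the evidence planned for it. A significant Group-by-baseline interaction supports a statement about how the drug difference varies with the baseline measure. It does not by itself support non-response to Intuniv, and it does not establish response to either drug in the other group.

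The invariance to an arm-wide shift is exact and needs no assumptions. The 48% (n=60) and 23% (n=30) at a true 0.5 SD improvement rest on the assumed effect sizes, residual SD and ROI correlation. In those trials the interaction is a correct finding about the drug difference; only the step from it to non-response would be wrong. This is a secondary objective and the model itself is sound, so the SAP should be changed in wording and reporting, not in design.

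**What to change.** Keep the moderation model and add the following to the SAP before analysis.

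1. Express each baseline ROI as a deviation from the healthy controls already scanned. Fix the deviation that counts as anomalous and the values that count as comparable to controls.
2. From the same fitted model, report the randomised Vyvanse–Intuniv difference, and each arm's mean impulsivity change, at those values with 95% confidence intervals.
3. State that a significant interaction supports only the conclusion that the drug difference in impulsivity change depends on the baseline reward measure, and reword the secondary objective to match.
4. Allow a statement of little or no improvement on Intuniv only if the upper 95% bound of the Intuniv-arm improvement lies below a margin that the sponsor fixes in advance. Describe it as change on treatment, not drug effect.

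A non-significant Intuniv-arm test should not replace item 4. With a true 0.5 SD improvement, such a test is non-significant in about 57% of trials at n=60 and 77% at n=30. With 0.5 SD as an illustrative margin, the bound in item 4 wrongly supports the statement in only about 2%.

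The cost is SAP text and linear contrasts, with no new patients, scans or model. The downside is a more modest conclusion. With that illustrative margin and a true improvement of zero, the non-response statement would be supported in only about 44% of trials at n=60 and 24% at n=30.
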